9.3.4 Subject Identification and Replacement

Each subject will be assigned a unique subject identifier, which will be on all eCRF pages. In legal jurisdictions where use of initials is not permitted, a substitute identifier will be used.

Subjects who discontinue the study will not be replaced.

9.3.5 Duration of Subject Participation

Subject participation will involve surgical implantation of the ICV access device followed by 14 to 28 days of post-operative recovery and will continue for at least 144 weeks of treatment for all subjects. Treatment will continue until all procedures are completed, the subject withdraws consent and discontinues from the study, is discontinued from the study by the investigator, or the study is terminated by BioMarin. A Safety Follow-Up visit will be conducted 6 months after the final BMN 190 infusion, but will not be required if the subject enrolls in an extension study, registry, or otherwise has continued access to BMN 190 within 6 months after the last infusion (refer to Section 10.2.1 for AE/SAE reporting instructions).

BioMarin reserves the right to discontinue the study any time for clinical or administrative reasons and to discontinue participation of an individual investigator or site for clinical or administrative reasons, including, but not limited to, poor enrollment or noncompliance with procedures of the protocol or GCP.

9.4 Treatments

BioMarin or its designee will provide the study site with study drug sufficient for study completion. BioMarin or its designee will be responsible for shipping study drug to clinical sites.

9.4.1 Treatments Administered

BMN 190 will be administered by ICV infusion every 14 days (\pm 3 days), preferably in the morning, according to the patient's age:

- birth to < 6 months: 100 mg
- 6 months to < 1 year: 150 mg
- 1 year to < 2 years: 200 mg (first 4 doses), 300 mg (subsequent doses)
- ≥ 2 years: 300 mg

BIOMARIN 190-2

190-203 Amendment 6

Patients younger than 2 years will start the study at the dose level appropriate for their age and will transition to the dose level consistent with their age as they mature.

Fasting for a minimum of 2 hours may be considered for the first infusion and subsequent infusions until the subject's reaction to the study drug is determined. When a feeding tube is used, the tube may be turned off 2 hours before infusion.

The normal infusion will be administered over 4 (± 1) hours at a rate of 2.5 mL/hr; the dose will be determined by the patient's age. Subjects not receiving the full 300 mg dose (administered in a total volume of 10 mL), will receive the appropriate volume at a rate of 2.5 mL/hr for over a shorter duration of time (see Table 9.4.1.1 below).

Age	Dose	Rate	Infusion Time	Dose Modification Options (AEs)
birth to < 6 months	100 mg	2.5 mL/hr	1.3 hours (±0.5 hr)	 Reduce infusion rate and administer drug over 2 hours Reduce the dose by 50% administered over the 1.3 (±0.5) hours Reduce the infusion rate and administer 50% of the target dose over 2 hours
6 months to < 1 year	150 mg	2.5 mL/hr	2 hours (±0.5 hr)	 Reduce infusion rate and administer drug over 3 hours Reduce the dose by 50% administered over the 2 (± 0.5) hours Reduce the infusion rate and administer 50% of the target dose over 3 hours
1 year to < 2 years	200 mg (first 4 doses),	2.5 mL/hr	2.7 hours (±1 hr)	• Reduce infusion rate and administer drug over 4 hours (200 mg); 6 hours (300 mg)
	300 mg (subsequent doses)	2.5 mL/hr	4 hours (±1 hr)	 Reduce the dose by 50% administered over the 2.7 (±1) hours (200 mg); 4 (±1) hours (300 mg) Reduce the infusion rate and administer 50% of the target dose over 4 hours (200 mg); 6 hours (300 mg)
≥2 years	300 mg	2.5 mL/hr	4 hours (±1 hr)	 Reduce infusion rate and administer drug over 6 hours Reduce the dose by 50% administered over the standard time of 4 (± 1) hours Reduce the infusion rate and administer 50% of the target dose over 6 hours

 Table 9.4.1.1: Age-Specific Dosing Schema for BMN 190 Administration

Dosing can be adjusted in the judgement of the investigator, upon consultation with the medical monitor, to manage AEs as outlined above. Should the dose-limiting AE resolve in

BIOMARIN 190-203 Amendment 6

the opinion of the investigator, and upon consultation with the medical monitor, dosing at the full dose may resume.

In patients younger than 2 years, dosing may also be adjusted by the sponsor in consultation with the investigator and medical monitor based on results from PK analysis, as follows:

- Within a patient, if the observed CSF AUC_{0-t} exceed the range of CSF AUC_{0-t} characterized with the 300 mg dose in Study 190-201, the dose may be reduced to 50% of the recommended age-appropriate dose.
- Within a patient, if the observed CSF AUC_{0-t} is less than the range of CSF AUC_{0-t} characterized with the 300 mg dose in Study 190-201, the dose may be increased to the recommended dose for the next oldest age group.

9.4.2 Identity of Investigational Product

9.4.2.1 Product Characteristics and Labeling

The study drug label includes, but is not limited to, the following information: lot number, required storage conditions, a precautionary statement, expiry date, study number, and BioMarin name and address.

9.4.3 Storage

At the study site, all study drugs must be stored under conditions specified in the Investigator's Brochure and Study Pharmacy Manual in a secure area accessible only to the designated pharmacists and clinical site personnel. All study drugs must be stored and inventoried, and inventories must be carefully and accurately documented according to applicable local, state, and federal regulations, ICH GCP, and study procedures.

9.4.4 Directions for Administration

Surgical implantation of an ICV reservoir will take place prior to study drug administration. The investigator will evaluate the patency, location, and skin integrity of the reservoir at each study drug administration (refer to the Study Pharmacy Manual). At each administration, the investigator will draw 1-2 ml of CSF into the device cannula to check for patency prior to administering the study drug. This volume of CSF is also to be used for laboratory testing (cell count, protein, glucose, and culture) as noted in Table 9.1.1. Access to the device is performed using strict sterile technique. Skin covering the reservoir is inspected for an appropriate needle insertion site. The needle insertion site must be intact, without evidence of breakdown, wound, infection or rash. The needle used is a small gauge non-boring tip. Once the reservoir has been accessed, the needle is immobilized to ensure minimal movement or risk of removal. If the needle dislodges during an infusion, it may not be reinserted, as sterility has been compromised. At the discretion of the investigator and/or neurosurgeon, the

BOMARIN

reservoir may be replaced during the clinical study. Refer to Section 7.4.2 for risks associated with the implantation procedure.

All study subjects will be administered BMN 190 by ICV infusion every 14 days (\pm 3 days), preferably in the morning. Fasting for a minimum of 2 hours may be considered for the first infusion and subsequent infusions until the subject's reaction to the study drug is determined. When a feeding tube is used, the tube may be turned off 2 hours before infusion. Study procedures for each study visit should precede study drug infusion unless otherwise specified. The date, time, volume, and concentration of each dose of study drug administered to each subject will be recorded in the dispensing log provided for the study as well as on the appropriate eCRF. The Study Pharmacy Manual provides further instructions on preparation and administration of study drug.

Subjects will be admitted to the hospital for every BMN 190 infusion. For all infusions, subjects will be monitored in an appropriate inpatient setting for a minimum of 24 hours from the start of the infusion. For the first infusion only, subjects will also return for a follow-up visit to clinic 72 hours (and no later than the third calendar day) after the start of infusion. After all visits, the parent or legal guardian will be telephoned within 48 hours to determine health status.

Because hypersensitivity reactions may be associated with ERT administration, subjects should be pretreated with age-appropriate doses of antihistamine (and antipyretic, if appropriate) medication approximately 30 minutes (\pm 15 minutes) before BMN 190 infusions. Subjects may be pretreated, at the discretion of the Investigator, with age-appropriate sedative medication approximately 30 minutes (\pm 15 minutes) before BMN 190 infusion according to institution's standard practices. Clinical, developmental, and QOL assessments are to be performed before premedication for infusions.

The normal infusion will be administered over 4 (\pm 1) hours at a rate of 2.5 mL/hr; the dose will be determined by the patient's age. Subjects not receiving the full 300 mg dose (administered in a total volume of 10 mL) will receive the appropriate volume at a rate of 2.5 mL/hr for over a shorter duration of time (see age-specific dosing table in Section 9.4.1). Uniform infusion rate should be ensured by use of a syringe pump with appropriate delivery range, delivery rate accuracy, and alarms for incorrect delivery or occlusion. If the dose needs to be stopped for safety or other reasons, it may be restarted at the same rate and completed so long as the total dose is administered within 10 hours of preparation of the dose syringes.

Dosing can be adjusted in the judgement of the investigator, upon consultation with the medical monitor, to manage AEs as outlined in Table 9.4.1.1. Should the dose-limiting AE

BIOMARIN 190-203 Amendment 6

resolve in the opinion of the investigator, and upon consultation with the medical monitor, dosing at the full dose may resume.

In patients younger than 2 years, dosing may also be adjusted by the sponsor in consultation with the investigator and medical monitor based on results from PK analysis, as follows:

- Within a patient, if the observed CSF AUC_{0-t} exceed the range of CSF AUC_{0-t} characterized with the 300 mg dose in Study 190-201, the dose may be reduced to 50% of the recommended age-appropriate dose.
- Within a patient, if the observed CSF AUC_{0-t} is less than the range of CSF AUC_{0-t} characterized with the 300 mg dose in Study 190-201, the dose may be increased to the recommended dose for the next oldest age group.

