7.4.1 Hypersensitivity Reactions

Hypersensitivity reactions, including anaphylaxis and less severe allergic reactions, are an identified risk for ERT in general, including BMN 190. Thus, anaphylaxis and less severe allergic reactions may occur during and following ICV infusion of BMN 190. Therefore, it is required that appropriately trained personnel and equipment for emergency resuscitation (including epinephrine) be available near the bedside during study drug infusion. For information regarding the reporting of hypersensitivity reactions, refer to Section 10.4.1.

An allergic reaction is a disorder characterized by an adverse local or general response from exposure to an allergen. Allergic reaction may include a combination of the following symptoms: flushing or rash, fever, urticaria, dyspnea, symptomatic bronchospasm with or without urticaria, allergy-related edema/angioedema, hypotension, or anaphylaxis. Infusion of BMN 190 may provoke additional symptoms of allergic reactions not included in this list. The investigator will categorize the severity of an allergic reaction as described in Section 10.2.3.2.

Anaphylaxis, a systemic, immediate hypersensitivity reaction, is the most severe form of hypersensitivity reaction. Symptoms may occur during or within hours following infusion of an agent and, generally, more rapid onset indicates more severe reaction; death may result. Managing anaphylaxis requires early recognition of signs and symptoms and clinicians well trained in the management of acute events. Symptoms of anaphylaxis may include involvement of skin and/or mucosal tissue (e.g., generalized hives, pruritus or flushing, swollen lips-tongue-uvula) respiratory compromise (e.g., dyspnea, wheeze-bronchospasm, stridor, reduced peak expiratory flow, hypoxemia), and reduced blood pressure or end-organ dysfunction (e.g., hypotonia, syncope, incontinence).

All AEs, including hypersensitivity, anaphylaxis and other allergic reactions that occur within 24 hours after infusion start or restart, regardless of the investigator's assessment of study drug relationship, will be considered to be temporally related events (TREs). It is expected that the TREs of greatest clinical importance will be hypersensitivity reactions, but not all TREs may be allergic in nature. The risk of such reactions may be mitigated by specific measures, including pretreatment or infusion modification, as described in Section 9.4.4.

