7.4.2 Risks of Intracerebroventricular Devices and Drug Administration

Patients in this study will be required to have an ICV reservoir surgically implanted for administration of BMN 190. An MRI will be performed in advance of the procedure to ensure proper planning and placement of the ICV access device. The ICV access device

BIOMARIN¹⁹⁰⁻²⁰³ Amendment 6

placement procedure will be performed under general anesthesia by qualified surgeons and will include placement of an endotracheal breathing tube during the procedure. Patients will be monitored closely in a nursing-intensive environment for 48 hours post-ICV device placement and after the start of the first drug infusion. Following ICV access device placement, subjects and their caregivers will be given written instructions providing details on signs and symptoms of concern for device complications and instruction on when to return to the site for device evaluation. An additional follow-up phone call will be conducted within 48 hours of inpatient discharge for all visits.

Risks associated with the procedure include sore throat, hoarseness, mouth pain, injury to the mouth or teeth, injury to blood vessels, aspiration and pneumonia. Although rare, unexpected severe complications with anesthesia can occur and include the possibility of infection, bleeding, drug reactions, blood clots, loss of sensation, loss of limb function, paralysis, stroke, brain damage, heart attack, or death.

Common side effects after the procedure include nausea, vomiting, dry mouth, sore throat, shivering, sleepiness, mild hoarseness, and pain.

The ICV access device will be available for first infusion ≥ 14 days after placement. First dose must take place within 28 days of placement.

The use of ICV access devices can result in infections, intracerebral hemorrhage, reservoir leakage, and seizures (Karavelis, 1996), (Kronenberg, 1998). Additional surgery may be required to fix or replace the devices. The technical complication rate of one ICV reservoir study in 106 cancer patients was 10.3% with almost half of these complications requiring surgical revision (median time reservoirs were in place was 4.1 months ranging from 2 days to 4.6 years) (Lishner, 1990). The current complication rate for BMN 190 administration is consistent with this large series report.

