Patients will be monitored throughout the study for potential infections (high temperature, cough, rash, headache, mental status changes, swelling or drainage in the incision area) and signs of ICV reservoir leakage or failure (refer to Section 9.7.5.2). Material degradation of the ICV device reservoir has occurred after approximately 105 perforations of the ICV device in benchtop testing, and has been observed in clinical trials with approximately 4 years of BMN 190 administration. Access device replacement should be considered prior to 4 years of regular administration of Brineura; with the decision made on an individual subject level based on the medical judgment of the Investigator. The CSF will be monitored for signs of infection at each infusion. If a device infection is confirmed, the site will confer with the sponsor and neurosurgical support to manage the intervention including potential device

removal, treatment with appropriate antimicrobial medications, and the suitability and timing of replacement and re-initiation of therapy.

All BMN 190 infusions are given in an inpatient setting with supportive measures present. For all infusions, patients will be monitored in an appropriate inpatient setting for a minimum of 24 hours from the start of the infusion. For the first infusion only, subjects will also return for a follow-up visit to clinic 72 hours (and no later than the third calendar day) after the start of infusion. After all visits, the parent or legal guardian will be telephoned within 48 hours to determine health status.

8 **STUDY OBJECTIVES**

The primary objectives of this study include the following:

- evaluate safety and tolerability of BMN 190 administered via intracerebroventricular (ICV) device
- to evaluate treatment effectiveness as a delay in progression of motor-language (ML) score on the Hamburg CLN2 clinical rating scale
- assess immunogenicity of BMN 190 in CSF and serum •

Secondary objectives of this study include the following:

- to characterize the pharmacokinetics of BMN 190 in CSF and plasma
- measure MRI parameters of disease progression •
- assess impact of treatment on the total Hamburg clinical rating scale
- assess the time to disease manifestation for asymptomatic patients

Exploratory objectives of this study include the following:

- assess development achievement •
- assess abnormal involuntary movements •
- evaluate retinal anatomy using optical coherence tomography (OCT)

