Some of the events that occur within the 24 hour period post-infusion may be hypersensitivity mediated. Hypersensitivity reactions are characterized by an adverse local or general response from exposure to an allergen. Symptoms of hypersensitivity reactions may include fever, chills/rigors, skin symptoms (urticaria, angioedema, rash), respiratory symptoms (dyspnea, wheezing, stridor), gastrointestinal symptoms (nausea, vomiting, abdominal pain) and/or cardiovascular changes (hypotension/hypertension).

In severe cases, anaphylaxis – a systemic hypersensitivity reaction – may also occur. Anaphylaxis is the most severe form of hypersensitivity reaction in which symptoms may occur during or within hours of an infusion; if anaphylaxis goes untreated, death may result. Symptoms of anaphylaxis may include involvement of skin and/or mucosal tissue (e.g., generalized hives, pruritus or flushing, swollen lips-tongue-uvula) respiratory compromise (e.g., dyspnea, wheeze-bronchospasm, stridor, reduced peak expiratory flow, hypoxemia), and reduced blood pressure or end-organ dysfunction (e.g., hypotonia, syncope, incontinence).

To date there has been no anaphylaxis or anaphylactoid reactions in studies with BMN 190. However, in the event of a suspected anaphylactic reaction, serious hypersensitivity event, or severe hypersensitivity (defined as a hypersensitivity event of Grade 3 or higher), blood samples to assess C4, serum tryptase, and total IgE will be collected within 1 hour of the event and tested; a blood sample to assess drug-specific IgE will be collected no sooner than 8 hours after the event (or before the next infusion).

In addition, the investigator must contact the BioMarin medical monitor (Section 10.8) within 1 business day if any AE is severe (Grade 3 or higher) or serious and requires any of the following:

BIOMARIN 190-203 Amendment 6

- infusion interruption, discontinuation, or modification (not due to blocked line)
- administration of IV fluids, steroids, or antihistamines
- administration of oxygen

Before subsequent infusions, the investigator and BioMarin medical monitor will discuss the case and agree upon infusion modification or additional premedication. Agreed upon dose modifications or introduction of additional premedication should be documented in the Case Report Forms and source files.

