Safety assessments will be conducted during and after each infusion. Subjects may be required to stay for a longer observation period at the investigator's discretion. If an AE consistent with a hypersensitivity reaction (Section 7.4.1) is observed, appropriate intervention may include infusion interruption, infusion rate decrease, or administration of antihistamine, oxygen, fluids, or steroids. If infusion is restarted after interruption, the initial rate should be approximately one-half the rate at which the reaction occurred. Further detail for infusion modification is provided in the Study Pharmacy Manual.

BOMARIN

The parent or legal guardian will be instructed to contact the investigator to discuss any AE subsequent to discharge.

The use of ICV access devices can result in infections, intracerebral hemorrhage from chronic reservoir use, reservoir leakage, and seizures (Karavelis, 1996) (Kronenberg, 1998). Additional surgery may be required to fix or replace the devices. Patients will be monitored throughout the study for potential infections (high temperature, cough, rash, headache, swelling or drainage in the incision area) and signs of ICV reservoir leakage or failure (refer to the Study Pharmacy Manual).

Because of the inherent safety considerations surrounding the implanted device, arrangements should be made for the subject to have the ICV access device removed no more than 4 weeks after either the Study Completion visit or the Early Termination visit. All removed or replaced implantable ICV devices must be returned to BioMarin in order to evaluate the material integrity of the reservoir, and all other devices (as described in the Pharmacy Manual) except for infusion pumps, should also be returned. If the subject intends to continue to receive BMN 190 following participation in this study (e.g., via commercial product, use in a registry, or another BMN 190 study), then the device does not need to be removed. Following device removal, subjects should return to the site 4 weeks (±3 days) later for a safety follow-up visit.

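### Protocol 9.4.4 permits a same-rate restart that 9.4.4.1 directs against after a hypersensitivity-type stop, and monitoring after the first infusion is given as both 48 and 24 hours

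*Protocol*

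**What the plan says.** **Restart after a stop.** Protocol 9.4.4 states: "If the dose needs to be stopped for safety or other reasons, it may be restarted at the same rate and completed". The only condition attached is "so long as the total dose is administered within 10 hours of preparation of the dose syringes".

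Subsection 9.4.4.1 takes up hypersensitivity: "If an AE consistent with a hypersensitivity reaction (Section 7.4.1) is observed, appropriate intervention may include infusion interruption, infusion rate decrease", among other measures. Its next sentence reads: "If infusion is restarted after interruption, the initial rate should be approximately one-half the rate at which the reaction occurred". It then refers to the Study Pharmacy Manual for more detail on modifying infusions.

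Two other places bear on this. Section 7.4.1 says of these reactions: "The risk of such reactions may be mitigated by specific measures, including pretreatment or infusion modification, as described in Section 9.4.4". Section 9.1 provides for severe or serious AEs that need certain interventions: "Before subsequent infusions, the investigator and BioMarin medical monitor will discuss the case and agree upon infusion modification or additional premedication".

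**Monitoring after the first infusion.** Section 7.4.2 requires close nursing-intensive observation "for 48 hours post-ICV device placement and after the start of the first drug infusion". The same sentence, with small variations, is in the synopsis, 9.1, Table 9.1.1 footnote k, 9.1.2 and 12.2. Footnote k, 9.1.2 and 12.2 make it a minimum.

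Section 7.4.2 also states: "For all infusions, patients will be monitored in an appropriate inpatient setting for a minimum of 24 hours from the start of the infusion". The synopsis, 9.1, 9.4.4 and 9.4.4.1 repeat this. Section 12.3.2.1, which covers Day 1 of the first infusion, sets a 24-hour inpatient minimum. Section 12.4 allows a stable subject to leave after 24 hours and applies this to all visits.

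**The concern.** A hypersensitivity stop is a stop for safety, so it falls under the general sentence in 9.4.4. That sentence neither excepts it nor points to 9.4.4.1. Staff who rely on 9.4.4 may restart at the rate that was running when the reaction occurred; staff who rely on 9.4.4.1 should start at about half of it.

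The monitoring text has the same fault. A site working from the Day 1 list in 12.3.2.1 may end observation at 24 hours. A site working from footnote k or 9.1.2 would, on the natural reading, keep the child for at least 48 hours. The described care setting differs as well.

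What is at stake is safety conduct in a population that includes infants: during a suspected hypersensitivity reaction, and after a first intraventricular dose. The situation is foreseeable, since section 7.2 lists hypersensitivity reactions among the common AEs in Study 190-201/190-202. No effect on an endpoint or an analysis is claimed.

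**Working it through.** **Restart: does other text settle it?**

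- Section 7.4.1 sends the reader to 9.4.4, and that section holds both sentences.
- The medical-monitor discussion in 9.1 comes before later infusions, so it does not govern a restart within the same infusion.
- Table 9.4.1.1 lists reduced rates for managing AEs but no restart rate. Its 300 mg option is 10 mL over 6 h: 10 / 6 = 1.67 mL/hr, or 1.67 / 2.5 = 0.67 of the standard rate. That is neither the same rate nor half.
- Section 9.3.3.1 names rate reduction as an intervention and gives no restart rate.

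**Restart: size of the difference.** Inputs are 300 mg in 10 mL, a standard rate of 2.5 mL/hr and the 10-hour limit (all 9.4.4), and the age-specific doses (Table 9.4.1.1).

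- Check on the protocol's own figure: 10 mL / 2.5 mL/hr = 4.0 h, matching the stated 4 h.
- Concentration: 300 mg / 10 mL = 30 mg/mL.
- Same rate: 2.5 × 30 = 75 mg/hr.
- Half rate: 1.25 × 30 = 37.5 mg/hr.

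The 10-hour limit could have settled the matter if a half-rate infusion could not finish in time. The last column below is an upper bound, with the half rate held for the whole dose.

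| Dose (mg) | Volume (mL) = dose / 30 | Time at 2.5 mL/hr (h) | Time at 1.25 mL/hr (h) |
|---|---|---|---|
| 100 | 3.33 | 1.33 | 2.67 |
| 150 | 5.00 | 2.00 | 4.00 |
| 200 | 6.67 | 2.67 | 5.33 |
| 300 | 10.00 | 4.00 | 8.00 |

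A more typical case is a 300 mg dose stopped after 1 h, with 7.5 mL left. Total pump time is 1 + 7.5 / 2.5 = 4 h at the same rate, or 1 + 7.5 / 1.25 = 7 h if the rest runs at half rate. All cases fit within 10 h. The longest leaves 10 − 8 = 2 h for preparation and the interruption. The time limit therefore does not choose between the two rules.

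**Monitoring: passages side by side.**

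| Duration | Setting described | Where stated |
|---|---|---|
| 48 h | Nursing-intensive | Synopsis, 7.4.2, 9.1, Table 9.1.1 footnote k, 9.1.2, 12.2 (six places) |
| 24 h | Appropriate inpatient | Synopsis, 7.4.2, 9.1, 9.4.4, 9.4.4.1 (all infusions); 12.3.2.1 (first infusion) |
| Discharge allowed after 24 h | Not stated | 12.4 (all visits) |

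The synopsis, 7.4.2 and 9.1 each carry both durations. The clearest clash is 12.3.2.1 against footnote k and 9.1.2: the same infusion, a different minimum and a different setting. The gap is 48 − 24 = 24 hours, once per subject, with at least 10 subjects planned.

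The 48-hour sentence names two events after one duration, so the natural reading applies 48 hours to both. If the duration belongs to device placement alone, nursing-intensive monitoring after the first infusion has no stated length. Either reading needs correcting.

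**The case against.** **On the restart.** A specific *should* can be read as qualifying a general *may*, and 9.4.4.1 sits inside 9.4.4. The general sentence follows text about syringe-pump accuracy and occlusion alarms. The next paragraph of 9.4.4 allows dose adjustment for AEs through Table 9.4.1.1. A half-rate restart breaches neither sentence, and the Study Pharmacy Manual may already give sites one clear rule. All of this is fair. But the general sentence names safety stops expressly, no text makes it yield to the subsection, and a clear manual would not remove the difference within the protocol.

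**On monitoring.** The 24-hour figures are floors, so a 48-hour stay meets every passage, and a general floor can coexist with a higher one for the first dose. Section 12.4 is headed as the two-weekly schedule, although it says all visits and its own ECG item mentions the first infusion. Five of the seven 24-hour statements repeat one sentence. What remains is 12.3.2.1, which is specific to the first infusion and gives the lower figure.

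**On consequence.** First-dose follow-up has several layers: daily AE assessment on Days 2 to 6, laboratory tests on Day 2, a 72-hour clinic return, and an examination and CSF sample on Day 6. These limit the harm from an early discharge but do not set the inpatient period. SAP 4.1.1 says all enrolled subjects had received study drug, so for them a correction to the first-infusion text comes too late. That limits its practical value but does not make the passages agree.

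**Conclusion.** Both inconsistencies hold.

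- **Restart:** for hypersensitivity-type stops only, 9.4.4 permits what 9.4.4.1 directs against. The difference is 75 versus 37.5 mg/hr if the reaction occurs at the standard rate. For other stops the passages do not clash.
- **Monitoring:** on the natural reading of the 48-hour sentence, a discharge 24 hours after the first infusion meets 12.3.2.1 and breaches footnote k, 9.1.2 and the matching passages.

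The conclusion rests on the protocol text alone, without the Study Pharmacy Manual. It takes no view on which rate, duration or setting is right. This should be fixed as a matter of safety conduct; it does not change any estimate, test or endpoint.

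**What to change.** - Reconcile 9.4.4 with 9.4.4.1 so that one restart rule covers hypersensitivity-type stops. State which rule covers other stops, and whether the 10-hour limit applies to both.
- Reconcile the 48-hour passages (synopsis, 7.4.2, 9.1, Table 9.1.1 footnote k, 9.1.2, 12.2) with the 24-hour passages (synopsis, 7.4.2, 9.1, 9.4.4, 9.4.4.1, 12.3.2.1, 12.4). The first infusion should have one minimum period and one care setting.
- Check that the Study Pharmacy Manual agrees with the result.

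The sponsor's clinical team decides which rules apply. The cost is a protocol wording clarification and a check of the manual, with no change to the design or the analysis.
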